3.4.3 Targeted Online National Campaign Led by Commando LLC

Additionally, we will work with our partner, Commando LLC to develop, launch, and execute a national ad campaign. Commando has experience with running successful advertising campaigns and will be working with us to develop social media strategy (including creatives and content such as In-Feed Videos, Reels, Facebook/Instagram Lives, Stories), providing technical support (landing page assistance), and analytics reporting (DMA analysis that provide powerful insights, such as which DMAs have higher conversion rates, engagement, and return on ads spends). They will be advertising on top

LGBTQ dating applications (e.g., Grindr, Growlr, Adam4Adam, Scruff, Jackd,) with whom they've been very successful in reaching YMSM for other studies.

3.4.4 Recruitment Limitations, Anticipated Problems and Alternative Solutions Consistent with

multi-prong approaches designed to reduce recruitment bias, we will employ the aforementioned recruitment methods. We will ward off potential recruitment problems by carefully monitoring each approach to prevent recruitment problems. This will involve weekly review of recruitment data with staff to assess efforts and reports provided by Commando LLC. In this way, the recruitment process will be a dynamic process involving actionable, data-driven insights to help us improve targeting, segmentation, and personalization to improve the recruitment experience for YTM.

3.5 Screening Procedures

3.5.1 Eligibility Screening Procedures

Potential participants will be electronically screened through REDCap(33) for eligibility using the full screening instrument. If a potential participant is screened and eligible and willing to participate, then they will voluntarily provide e-assent/consent. If it is determined during enrollment that a person is concurrently enrolled in another HIV prevention study, they will be deemed ineligible.

3.5.2 Verification of Identity and Initial Screening Criteria

We will use the following procedures to verify the race, sex, and age of participants, and ensure that participants are discrete, not duplicated, and to document the country of residence, for example, individuals living in the U.S. or its territories): 1) Prior to signing the electronic assent/consent form for trial participation, participants are asked to do a confirmatory screening visit via videoconferencing during their baseline phone call to confirm race, sex, and age. If participants become ineligible, we let them know that, unfortunately, we cannot continue with the visit because eligibility has changed; 2) To cross-check age, participants are asked their date of birth; 3) Participants are required to show any form of photo ID during the initial video conference so we can verify identity. If a participant does not have a government or school issued ID, we will ask them to furnish a report card/transcript with their legal name, age, and sex; 4) We will use 2 methods to verify participants' residence: a) We will ask participants to share a form of ID which includes an address, and b) we will cross-check the address on the ID with the IP address that we collect through REDCap software. If there is a discrepancy, we will review with the study participant to better understand if there is a rationale (e.g., participant is in college,). Using procedures previously piloted, we will determine co-enrollment.

3.6 Informed Assent and Consent

At the enrollment visit we will collect written informed e-consent (18 to 25 year olds; assent for 15 to 17 year olds) (see **Appendix A**) for study trial participation, which will detail purpose of trial, study procedures, compensation for contributed time, risks, benefits, site contact information, confidentiality and voluntary participation. The consent process also details the trial and study compensation. YMSM will then be randomized to the intervention arm (MyPEEPS Mobile) or control (delayed intervention) arm.

4.1 STUDY PROCEDURES

4.2 Enrollment Procedures

When a participant screens eligible, a study team member will schedule a visit through a videoconference call using Zoom. These procedures ensure the integrity and success of the study because: 1) We are able to eliminate fraud by verifying participants' identities via videoconference, fraud being a potential problem in online research,(34, 35) and 2) We establish rapport with our study participants and have seen very high retention rates related to this rapport building between our staff and study participants, which will be augmented by electronic retention strategies in this study.

4.3 Locator Form/Contact Information

At enrollment, participants will be asked to provide contact information to contact them throughout the duration of study for follow-up assessments. This information will be captured in REDCap may be updated during follow-up assessment and/or whenever the participant needs to update their contact information on file. We will collect each participant's cell phone number, email address, as well as encourage them to share their social media handles (e.g., Snapchat, Instagram, Twitter Facebook, WhatsApp, and/or Skype usernames). Participants will be asked if it is okay to mention the name of the project and method(s) of study communication preferred when receiving automated reminders (e.g., text messaging, email, phone call, leave voicemail). Study staff will not send messages or leave voicemail messages unless expressly permitted to do so by the participant. If permission is given to leave voice messages, site staff will assure participants that messages left will not include any protected health information or information related to study participation. If permission is given to send text messages and/or if study staff is unable to get in contact through email, staff will send text messages using an IRB-approved messaging script to contact participants throughout the duration of the study. Contact information will be maintained using the same confidential data management practices used for all study data.

4.4 Specific Aim 1 Procedures.

Specific Aim 1: Using qualitative methodology, expert feedback, and usability assessments, develop MyPEEPS Mobile for YTM.

MyPEEPS was built on considerable formative work with multi-racial and ethnic groups (R34MH079707; PI: [name] and U01MD011279; MPIs: [name] and [name]). Findings from the U01 have been peer-reviewed and published.(27, 36-40) In preparation for this R34, we conducted extensive preliminary work to identify the common themes, concerns, and HIV risk and protective factors in YTM to expand MyPEEPS and ensure its acceptability for this group, *particularly for YTM who are multi-racial or come from communities of color. This will be done* using the focus group data collected from 49 YTM in our preliminary work for this application, and through the feedback by our Expert Review Panel and usability testing with YTM.

Expert Review Panel. The goal of this panel is to reach censuses on common concerns, risk, and protective factors for YTM.

Procedures. The expert and youth advisory panels provided feedback remotely by reviewing the curriculum and providing written comments.

Development of mobile delivery technology. Following the expert panel sessions and building on our findings from our formative focus groups, we will develop mock-ups of a MyPEEPS Mobile App with our

partners at One Cow Standing, a software development company (see Letter of Support). The mockup will have partial functionality of the system and enable us to test the design. MyPEEPS Mobile for YTM will be novel, innovative, scientifically sound, scalable, translatable, and likely to have a strong public health impact, as detailed in the Innovation section. [name] will oversee all updates to the content of the MyPEEPS Mobile App, with support from MPIs Drs.

[name] and [name]. *The final product of this work will be a Beta version of the app for usability testing.*

Refinement of the MyPEEPS Mobile. Following the development of MyPEEPS Mobile for YTM, we will conduct usability testing. **Usability Testing.** The goal of usability testing is to improve the design and increase the likelihood of technology acceptance. We will evaluate the user interface and system functions of the MyPEEPS Mobile App and assess whether they are consistent with the end-users' needs. We will conduct two types of usability assessments: A) **Heuristic Evaluation** and B) **End-User Usability Testing.**

Heuristic Evaluation. Sample: Five informaticians with training in human-computer interaction and who have published in the field of informatics will be recruited as usability experts. Nielsen recommends using three to five evaluators since one gains little additional information by using larger numbers(41). We will recruit them through direct contact with the Informatics Departments at Columbia University and Weill Cornell Medical College, both of which have a large cadre of informatics researchers. [name] will send a message to potential evaluators via email using the MyPEEPS Heuristic Email Recruitment Script.

Procedures: The heuristic evaluator will be consented using the Heuristic Evaluation Consent form. Once consented, the heuristic evaluators will assess a web-based Beta version of the MyPEEPS Mobile App remotely via Zoom software. Evaluator screen movements and audio will be recorded via Zoom. Identifiable characteristics, such as facial features and names, will not be recorded. Similar to procedures that we have used in our prior work(42-44), each evaluator will be asked to evaluate the system using the Heuristic Evaluation Checklist and to think-aloud while performing the usability testing(45).

Participants will be asked to say aloud what they are thinking, seeing, and trying to do while they are performing the tasks required for the scenarios. When a user finds errors or the researchers find critical incidents that are characterized by comments, silence, or looks of puzzlement, the researcher will record the users' activities.

Recording the users' interactions and vocalizations provides additional feedback that can highlight problems that would not be identified with static screen shots(46). Each evaluator will walk through the use case scenarios (see "MyPEEPS Heuristic UseCaseScenarios Procedure 11.16") and a study team member will navigate through the app per evaluator instructions to complete the assigned tasks. Once the walkthrough is complete, the evaluator will fill out the Qualtrics survey titled, "Heuristic Evaluation Survey." After the heuristic evaluation, participants will be asked to rate the prototype's perceived ease of use and perceived potential usefulness using a standardized instrument. Instrument: Nielsen(47) proposed a list of ten recommended heuristics for a usable interface design. Each heuristic will be evaluated by one or more items, and the overall severity of the identified heuristic violations will be rated.(48) Evaluators will also complete the Health Information Technology (IT) Usability Evaluation Scale (Health-ITUES) to rate usability. This tool varies from most traditional measurement scales in that it is designed to support customization at the item level to match the specific task/expectation and health IT system while retaining standardization at the construct level. The Health-ITUES supports evaluation of three levels of task/expectation: user-system, user-system-task, and user-system- taskenvironment. [name] (MPI) has published on the usefulness of the Health-ITUES for evaluating the usability of mHealth technology(53). Data Analysis: The frequencies of usability issues will be calculated according to the heuristic principles adapted from Nielsen's checklist.

Mean severity scores will be calculated for each heuristic principle. Evaluators' comments about usability

problems on the evaluation form and the recording will be grouped and content analyzed according to the usability factors of Nielsen's heuristics.(49) Recordings will be kept until data analysis is complete and findings have been disseminated. Heuristic evaluators will be compensated a \$150 Amazon gift code for their time and will receive the gift code via email using the Heuristic Evaluator / Usability Compensation Email Template.

Usability Testing with YTM. We will conduct usability testing with YTM to identify violations of usability principles and any potential obstacles to their effective use and content of intervention adaptation of MyPEEPS Mobile with members of our advisory board of transmasculine youth. This is an iterative process that involves testing the system and then using the results to change it to better meet users' needs. Sample: We will recruit 20 YTM (15-25 years old) who will participate remotely in the formative evaluation of the prototype user interface screens. The rationale for 20 participants is based on past usability research, which has indicated that 95% of usability problems can be identified with 20 users(50). These youth will serve as community voices, specifically youth as advisors. We will purposely sample our usability testing participants to ensure diversity regarding race, ethnicity, and age. We will be recruiting by reaching out to participants in our REDCap database who previously expressed interest in the study or participants who are enrolled in another one of our studies. When we reach out to these participants in REDCap, we will be using the MyPEEPS Participant Outreach Script. We will also be using flyers for recruitment, once approved by the IRB. Participants will be screened for eligibility using the Usability Screener in REDCap. Procedures: We are requesting a waiver of documentation of consent for online screening procedures. The screening information will only be kept electronically in REDCap, which is a secure, CUMC approved system. If participants screen eligible, study staff will go through the informed consent process with participants. If participants consent to participate, they will complete the Assent/Consent form for Usability Testing. Participants will complete a brief demographic background and computer usage survey.

Participants will use a web-based beta version of the MyPEEPS Mobile with screen movements and audio recorded via Zoom software. Identifiable characteristics, such as facial features and names, will not be recorded. After the usability evaluation, participants will be asked to rate the prototype's perceived ease of use and perceived potential usefulness using a standardized instrument. Instrument: We will measure self-reported ease of use and usability with the Health Information Technology (IT) Usability Evaluation Scale (Health-ITUES)(51, 52). Data Analysis: The analysis will be based on the recordings of user sessions, transcriptions, notes, and the user surveys, and mean task performance time will be calculated. [name] will search for critical incidents which will be characterized by comments, silence, and repetitive actions. [name] will review these incidents in detail using Zoom software. The incidents will be identified, and the users' written comments summarized. Content analysis, a technique for making replicative and valid inferences from data, will be performed by the research assistant under [name]'s supervision. The comments will be categorized according to the positive characteristics, negative characteristics, and recommendations made by the end- users. Results from the standardized surveys will be analyzed using SAS 9.4 (SAS Institute, Cary NC) to calculate the descriptive statistics to complement the findings from the usability assessment. Using the findings from these activities, we will refine MyPEEPS for use in Aim 2. Recordings will be kept until data analysis is complete and findings have been disseminated. Participants will be compensated for their time in the form of a \$40 Amazon gift code and will receive the gift code via email using the Heuristic Evaluator / Usability Compensation Email Template.

4.5 Specific Aim 2 Procedures.

Specific Aim 2: Conduct a pilot randomized controlled trial to examine the feasibility, acceptability, and preliminary efficacy of the MyPEEPS Mobile App for YTM in a sample of 80 YTM (15-25 years) and refine the study methods for a future efficacy trial.

Overview. We will conduct a 6-month randomized controlled pilot study with 80 YTM. The goals of the pilot study are to: a) Gain direct feedback from participants about whether and to what degree the MyPEEPS Mobile App worked as intended; b) Assess the acceptability of MyPEEPS Mobile dosing and content for YTM; and c) Observe the flow of procedures, including assessment at baseline, retention efforts, data management, and follow-up assessments. The recruitment plan, screening, and consent/assent processes are described in the Protection of Human Subjects and Clinical Trials Information sections. Our **primary outcome for this study will be:** change in number of condomless receptive anal or vaginal sex acts with sex partners assigned male at birth. **Sampling Approach to Successfully Enroll YTM in this Project.** We will recruit 80 participants from an online national sample and ensure that at least half of our sample is from racial/ethnic minority groups. Using active and passive recruitment methods, the on-site project coordinators will oversee and participate in recruitment efforts. The study staff hired for this project, on-site coordinator, and the peer-to-peer networking efforts will be used to recruit study participants. Our pilot study will comprise a convenience sample through active online recruitment through Instagram, Twitter, Snapchat, and Facebook advertisements. We will use psychographic targeting (in-depth, publicly available consumer data such as interests, city) to advertise only to potentially eligible individuals. We have successfully used this approach to recruit our sample of YMSM in the MyPEEPS project. Through our advertisements, and as previously mentioned, we have screened

>800 YTM who would be eligible for the proposed MyPEEPS study, *and we will plan to recruit them as well as others into the proposed study. We are confident in our ability to enroll the proposed target sample.*

Sample Size and Power Calculation. This study plan is to enroll 80 participants with 1:1 random assignment to the intervention arm and the control arm (i.e., 40 in each arm). Compared to a large-scale randomized trial, we do not expect that this pilot trial will have power to detect many of the

effects that would be of scientific or have policy significance. This is consistent with the aims of this pilot grant mechanism, where budgetary limitations necessitate small sample sizes. Group means on continuous variables typically begin to stabilize by 20-30 subjects. Thus, a sample size of 40 participants per group should provide relatively stable group means for the intervention and control conditions, even with some sample attrition.

Potential Problems/Alternative Solutions Regarding Recruitment. Consistent with the multi-prong recruitment approach designed to reduce recruitment bias(54, 55), our team will carefully monitor each approach to prevent recruitment problems. This will involve weekly review of recruitment data with staff to assess efforts. In this way, recruitment will be a dynamic process and will reach the proposed diverse group of YTM.

[figure not shown]
Eligibility Screening and Informed Assent/Consent. See Protection of Human Subjects.

Study Enrollment. A baseline visit will be conducted involving a behavioral assessment and will last approximately 1.5-2 hours. YTM will then be randomized to the intervention or delayed intervention arm. An enrollment project will be created in REDCap to collect and manage data for enrolled participants. The longitudinal study module, automatic survey invitations, and secure file upload capabilities can be used in conjunction with customizable reports to ensure streamlined operations and efficient data management. Eligible volunteers will be scheduled for a one-time

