6.1 PARTICIPANT TRACKING & CLINICAL MANAGEMENT

6.2 Retention Efforts

Study staff will track retention, which will be reviewed weekly by the PIs. As has been successful in previous studies with this population, including the MyPEEPS Mobile efficacy trial, we will: 1) obtain, at baseline, participants' email addresses, phone numbers, social media handles, as well as the addresses and contact information of people participants believe could help us locate them in the future; 2) allow for any time of day, and all days of the week, for participants to complete online assessment visits; 3) provide participants with numerous methods for contacting study staff, including providing study phone numbers, email addresses, and social media handles and if agreed to by the participant, having them program our site numbers into their mobile phone during the enrollment visit; 4) routinely verify participants' locator information at every contact point; 5) if correspondence is returned indicating a participant no longer has a given email address, study staff will telephone to obtain their new email address; 6) if the phone number is disconnected, we will contact them via their social media accounts and/or individuals listed in participants' records; and 7) if participants are not responsive after 5 email correspondence attempts and/or have given permission to message them via phone number, we will attempt to make contact using participants' phone numbers using IRB-approved scripts. We will make every effort to maintain contact with participants, even if they move or discontinue the intervention, for those still willing to complete follow-up assessment visits. Given the older study population proposed in this trial, we are confident we will retain at least 80% of the study population for this study proposed in this trial, we are confident we will retain at least 80% of the study population for this study.

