8.2.2 Parental consent

Consistent with our prior studies in this population, we will not require parental consent for study enrollment. Parental consent may decrease participation rates because some youth (17-year-olds) will fear that they may be "outed" as a result of participation. Disclosure of sexual orientation or gender identity may place participating youth at risk for parental harassment, abuse, or expulsion from the home. The nature and scope of the proposed research do not pose more than "minimal risk" to participants, or that "the probability and magnitude of harm or discomfort anticipated in the research are not greater in and of themselves than those ordinarily encountered in daily life or during the performance of routine physical or psychological examinations or tests" (45 CFR Part 46.102). Study measures are standard in this population, as are waivers of parental permission for survey and interview studies.

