8.7.1 Confidentiality of Study Data

We have developed systematic protocols for data handling and storage over multiple cohort studies. To protect the integrity of the participant's data, the RA will assign each participant a unique PID at study enrollment. This code number will be used for all study data. We will maintain a list of participants with links between identifying information and code numbers for the sole purpose of avoiding any duplication in completion of the survey. Only the PIs, RAs, and Project Director will have access to these lists, which will be kept behind double-locks or on a secure server with password protected access. Computer files consist of the tracking database (REDCap), and study data files downloaded from the database. Tracking files are maintained in a highly secure scheduling and monitoring database which both sites can access. This database contains all contact information and is used to schedule and track study visits; it is completely password protected and user access and privileges will be managed by the data manager and Project Director. The tracking database stores contact preferences including information the participant agreed to provide for the purposes of tracking and communication; all communications strictly follow the participants' contact limitations. Data files are exported from REDCap and imported into the SPSS database for storage and analysis. Computer data files never have any identifying information and are encrypted for transfer between study sites. Data files do not include information that could be used to identify the participant from the data file alone. Columbia University will provide a standards-compliant (HIPAA, HHS Cybersecure) private cloud server for the hosting of application content and user data for the duration of the application deployment. This is a secure system and will be further protected by login credentials for limited access to protect participant confidentiality. Participants will also be encouraged to choose a private location to program a password for the application and complete the intervention modules for additional security. They will be prompted to log-out of the website after completing or progressing through any given module.

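### The contact rules forbid messaging without permission, yet let e-mail failure alone trigger a text or phone contact

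*Combined protocol and SAP*

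**What the plan says.** Section 4.3 makes permission a precondition: "Study staff will not send messages or leave voicemail messages unless expressly permitted to do so by the participant". Section 8.7.1 supports it in general terms: "all communications strictly follow the" contact limitations of the participant.

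Two sentences after the permission rule, section 4.3 turns to texting. The sentence opens with the case where permission to text has been given, then continues "and/or if study staff is unable to get in contact through email, staff will send text messages using an IRB-approved messaging script".

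Section 6.2, item 7, is built the same way: "if participants are not responsive after 5 email correspondence attempts and/or have given permission to message them via phone number", staff will try to reach them on their phone number with IRB-approved scripts.

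Item 6 of section 6.2 is a separate step. If the phone number is disconnected, "we will contact them via their social media accounts and/or individuals listed in" the participant's record. Item 1 explains where those individuals come from: at baseline staff collect the addresses and "contact information of people participants believe could help us locate them in the future".

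The only rule on message content is in section 4.3 and covers voicemail left with permission: "messages left will not include any protected health information or information related to study participation".

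Section 3.2.2 confirms that participants aged 15-17 are included. Section 8.2.2 waives parental consent and gives a reason: "Disclosure of sexual orientation or gender identity may place participating youth at risk for parental harassment, abuse, or expulsion from the home".

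**The concern.** A coordinator needs one answer to a simple question: may I text someone who has gone quiet on e-mail and never agreed to texts? The permission sentence says no. The next texting sentence and the retention procedure say yes. Because the same 'and/or' appears in two sections, it is hard to dismiss as a single slip.

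What is at stake is participant protection. The conflict arises only for people who did not permit the channel, who are the people the permission rule exists to protect. Some may be minors taking part without a parent's knowledge, in a protocol that acknowledges what disclosure at home could mean for them. Sample size, the primary outcome and the analysis are unaffected.

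**Working it through.** There is no figure to reproduce. The check compares the rules as conditions. Let P mean that the participant has permitted texts or phone messages, and E mean that e-mail contact has failed (in item 7, no response after five attempts).

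- Rule A (section 4.3, permission sentence): message only if P.
- Rule B (section 4.3, texting sentence): text if P or E.
- Rule C (section 6.2, item 7): contact by phone number if P or E.

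Rules B and C use the ordinary inclusive sense of 'and/or'.

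| P | E | Rule A | Rules B and C | Consistent? |
|---|---|---|---|---|
| yes | yes | allowed | contact | yes |
| yes | no | allowed | contact | yes |
| no | no | forbidden | no contact | yes |
| no | yes | forbidden | contact | **no** |

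Three of the four cases agree. The fourth is a direct contradiction, and it goes away only if 'and/or' is read as 'and'.

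Two details sharpen this:

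1. Rule A is about messages and voicemail. A live call under item 7 would not breach Rule A as worded. It would breach section 8.7.1 if the participant had ruled out the phone. A text or voicemail breaches Rule A, and also section 8.7.1 if the participant had set that limit.
2. The fourth case can occur in ordinary follow-up. Section 4.5 sends survey invitations by e-mail with up to five automated reminders, and lets participants choose texts and/or e-mails for intervention reminders. An e-mail-only participant is therefore foreseen. Whether the automated reminders count towards the five attempts in item 7 is not stated.

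Item 6 lies outside this table. Its trigger is a disconnected phone, not P or E. What can be said of it is limited: no script or content rule is given for contacting social-media accounts or listed individuals, and the locator data listed in section 4.3 do not include those individuals.

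**The case against.** The strongest reply is that this is loose drafting that sensible staff would resolve correctly. The permission sentence comes first, section 8.7.1 covers all communications, texts go to the participant's own number under a script the IRB has approved, and participants are asked whether the project name may be mentioned in automated reminders. Most of that stands, and it limits the likely harm. It does not settle the conflict. Section 8.7.1 states a principle but does not say that it overrides the steps in section 6.2, and section 4.3 contains both rules.

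Some stronger readings are tempting but unsupported:

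- **That the 'and/or' wording sends staff to relatives or other third parties.** It does not. Item 6 has its own trigger, its contacts are named by the participant, and the social-media handles are volunteered. E-mail silence alone does not lead there.
- **That minors would be exposed to their parents.** The text of the script is not in the documents, and nothing says that parents would be contacted. The waiver argument in section 8.2.2 concerns disclosure caused by seeking parental consent, not retention contacts. Disclosure remains a possibility and is not a demonstrated consequence.
- **That the reported retention rate would be distorted.** Nothing shows that staff would diverge in practice, and no effect on the 80% target can be derived.

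**Conclusion.** The contradiction is real and should be corrected. It occurs within section 4.3, recurs in section 6.2 item 7, and both instances run against section 8.7.1. It rests on one reading: that 'and/or' carries its usual inclusive meaning.

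Its size is one conflicting case out of four. The number of people in that case cannot be estimated. A reader might start from the 80% retention target, which allows 20% of 80 = 16 participants not retained, and apply a guessed share who withheld permission. The documents give no such share. Nor are those 16 the same as e-mail non-responders, since section 6.5 lists other reasons for leaving, such as withdrawal of consent or incarceration. The number of minors is not given either.

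The case for correction does not need a count. The protocol makes a confidentiality promise and then directs staff to act against it, in a population that includes minors enrolled without parental consent. The gap in item 6 is secondary: a missing content rule, with no contradiction.

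**What to change.** 1. **Section 4.3.** Delete e-mail failure as a trigger in its own right, so that texts are sent only to participants who have permitted them. Do not require e-mail failure as well, because that would block the text reminders participants may choose under section 4.5.
2. **Section 6.2, item 7.** Replace 'and/or' with 'and', so that moving to the phone number needs both five unanswered e-mails and permission for that channel.
3. **Section 6.2, item 6 (secondary).** State that contact through social media or participant-named individuals is subject to the contact limitations in section 8.7.1, and to the same ban on study information that section 4.3 applies to voicemail.

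The cost is a wording change in two sections, with the permissions recorded by channel on the existing REDCap locator record. The downside is that a few non-responders who refused other channels may be lost to follow-up.
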